6.9 Criteria for Premature Study Termination for Phase II Study

Patients will be enrolled on the study as outlined above. If, at any time during the study, there is sufficient evidence suggesting an excessive Grade 3 or Grade 4 toxicity rate related to treatment, the study will be terminated. An excessive Grade 3 toxicity rate will be taken to be 20% (or 4 patients) and an excessive Grade 4 toxicity rate will be taken to be 10% (or 2 patients) of the patients enrolled to that date. Evidence that the toxicity rate is excessive will be considered sufficient if the lower limit of the 90% one-sided confidence interval for the estimate of the toxicity rate exceeds the appropriate limit (20% for Grade 3, 10% for Grade 4).

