6.1.1 Phase II Randomized Double Blind Placebo Controlled Study

Phase II study will consist of a randomized double blind placebo controlled study involving patients who have treatment interruption due to grade 2 or 3 irAEs. Patients may receive steroids at the discretion of the treating physician prior to and during treatment with CD24Fc. As the steroids is the most commonly used SOC therapy for irAEs and it affects the severity and duration of irAE, we will separate the subjects into two groups based on the status of steroids use at registration. Each group of patients will be randomized (1:1) to receive CD24Fc vs placebo in addition to SOC treatment for irAE. Patients who are randomized to treatment with CD24Fc will receive treatment every 2 weeks for total of three treatments. Placebo group will receive 100 mL of normal saline every 2 weeks for total of three treatments. Refer to [Table 2](#) and [Figure 2](#) for treatment schedule. All patients shall complete 3 treatments.

Two weeks after completing the third treatment dose, patients will be re-evaluated for retreatment with ICI at the discretion of the treating physician and post treatment re-evaluation. Thereafter, patients will continue to end of treatment safety follow up on day 60. After the end of treatment, we will follow patients with irAE and survival by chart check every 3 months for up to 1 year.

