10.3 Sample Size Justification

Phase I study: We plan to enroll 6 patients in the phase I study. The objective of this phase I study is to confirm the safety of CD24Fc in ICI-treated cancer patients who have treatment interruption due to grade 2 or 3 irAEs and to estimate the median time to recovery and resumption of ICI after treatment interruption due to irAE. The primary endpoint is new AE of \geq grade 3 that are outside the spectrum of irAEs when CD24Fc is given to treat irAEs. We expect the rate of this event will be less than 33.3%. With a sample size of 6 patients, we would have 74-91% chance to observe at least one occurrence if the true event rate is 20-30%. Hence the sample size is adequate for this pilot study for safety.

Randomized phase II study: Previous studies suggested that recovery rate at 42 days for control group will be about 50% [22, 56]. We hypothesize CD24Fc will increase recovery rate from 50% to 80 %. A sample size of 72 patients (36 in each arm) will have 81% power to detect an increase of response rate from 50% of control group to 80% of CD24Fc group. This result is based on one-sided Fisher's Exact test and significance level of 0.05.

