10.4 Safety Monitoring and Stopping Rule

The Phase II study is a randomized, double blind, placebo-controlled study. To ensure the safety of the patients enrolled in the Phase II study, Bayesian stopping boundaries are used to allow early stopping at any given time in the combined population. The objective response rate (ORR) and toxicity of CD24Fc during the whole study will be monitored simultaneously using the Bayesian stopping boundaries calculated based on beta-binomial distribution. Toxicity is defined as new AE of \geq grade 3 that are

outside the spectrum of irAEs. ORR is defined as partial response and complete response by RECIST V1.1 after retreatment with ICI.

The regimen will be considered safe if the ORR is at least 20% in all patients in both arms and the toxicity rate is maintained at most 33.3% for the CD24Fc arm. Previous studies for controls suggested the ORR after retreatment with ICI is about 20-40%, and therefore we consider a response rate <20% in all patients in both arms as unacceptable, which will indicate an effect of CD24Fc on promoting tumor growth. The prior probabilities of response and toxicity for the regimen are modeled by beta distributions [Beta(0.8, 1.2) and Beta(0.3, 1.7), respectively], and response and toxicity are assumed to be independent. Denoting the probabilities of response for both arms and toxicity for CD24Fc arm by $\{\theta_{RES}, \theta_{TOX}\}$, and they are compared to fixed targets of response and toxicity rates. The following decision criteria will be applied:

- 1) stop if $\text{Prob}\{\theta_{RES} < 0.2 \mid \text{data}\} > 0.97$, and
- 2) stop if $\text{Prob}\{\theta_{TOX} > 0.333 \mid \text{data}\} > 0.97$

We will have randomization box of 6 patients and thus ensure that 3 patients have been dosed for each 6 subjects enrolled. Patients will be monitored by a cohort size of 6 patients (3 for the CD24Fc arm and 3 for the placebo arm) according to the following stopping boundary for toxicity during the whole study. To be conservative, we attribute all AEs to CD24Fc.

Number of Patients Evaluated in All Enrolled Patients (half control and half CD24Fc)	Stop if Number of ORR Observed	Stop if Number of AE Observed
6	Never stop with these many patients	Never stop with these many patients
12	Never stop with these many patients	≥ 5
18	0	≥ 7
24	≤ 1	≥ 8
30	≤ 2	≥ 10
36	≤ 2	≥ 11
42	≤ 3	≥ 12
48	≤ 4	≥ 14
54	≤ 5	≥ 15
60	≤ 6	≥ 16
66	≤ 7	≥ 17
72	Always stop with this number of patients	

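### The Section 6.9 confidence-bound rule pools placebo patients into the denominator, tests Grade 3 and Grade 4 separately and omits Grade 5, which leaves CD24Fc-related severe or fatal toxicity inside the irAE spectrum weakly monitored

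*Combined protocol and SAP*

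**What the plan says.** Section 6.9 terminates Phase II if "there is sufficient evidence suggesting an excessive Grade 3 or Grade 4 toxicity rate related to treatment". It gives two limits. For Grade 3: "An excessive Grade 3 toxicity rate will be taken to be 20% (or 4 patients"). The Grade 4 rate "will be taken to be 10% (or 2 patients) of the patients enrolled to that date". Evidence is sufficient when "the lower limit of the 90% one-sided confidence interval for the estimate of the toxicity rate exceeds the appropriate limit", with 20% applied to Grade 3 and 10% to Grade 4. The interval method is not named, and Grade 5 does not appear.

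Section 6.1.1 sets the allocation: "Each group of patients will be randomized (1:1) to receive CD24Fc vs placebo in addition to SOC treatment for irAE". Section 10.3 plans 72 patients, 36 per arm.

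Section 10.4 has a second Phase II toxicity rule, under which the regimen is considered safe if "the toxicity rate is maintained at most 33.3% for the CD24Fc arm" (alongside a response criterion). It counts new AEs of grade 3 or higher outside the irAE spectrum, so deaths of that kind are included. It uses half of the enrolled patients as denominator and charges all AEs to CD24Fc. Neither section refers to the other.

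**The concern.** A toxicity rule in a placebo-controlled trial should respond to what happens on the drug. Three features of 6.9 work against that.

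- **Denominator.** If related events fall only on CD24Fc, 20% and 10% of all enrolled correspond to about 40% and 20% of CD24Fc patients.
- **Separate grades.** A mixture of Grade 3 and Grade 4 can stay under both limits.
- **No Grade 5.** Section 11.0.0 defines Grade 5 as its own category, so a related death enters neither rate. Section 4.1 lists Grade 5 as a Phase I DLT, and 10.4 counts grade 3 or higher, so 6.9 departs from the protocol's own practice.

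Section 10.4 excludes the irAE spectrum. Section 5.0 enrols patients with colitis, pneumonitis, renal, hepatic and skin irAEs, and Section 1.0 says irAEs can affect any organ. For related toxicity of those kinds, 6.9 is the only numerical Phase II stopping rule.

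**Working it through.** **Inputs.** From 6.9: limits 20% and 10%, one-sided 90% lower bound, all enrolled as denominator. From 6.1.1 and 10.3: 1:1, 72 patients. From 10.4: prior Beta(0.3, 1.7), limit 33.3%, posterior threshold 0.97. Assumptions: Clopper-Pearson interval; each patient counted once at worst grade; related events only on CD24Fc unless stated.

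**1. The plan's own counts.** 4/0.20 = 20 and 2/0.10 = 20, so the bracketed counts equal the percentages only at n = 20. The lower bound L(x, n) is the 10th percentile of Beta(x, n − x + 1). L(4, 20) = 9.0% and L(2, 20) = 2.7%, so neither count meets the confidence-bound sentence at n = 20. Four patients exceed the 20% bound only up to n = 9, and two exceed the 10% bound only up to n = 5. At 72 enrolled, 20% is 14.4 patients and 10% is 7.2.

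**2. Smallest counts that stop under the confidence-bound sentence.** At 12 enrolled, L(4, 12) = 15.4% and L(5, 12) = 21.9%, so Grade 3 stops at 5. L(3, 12) = 9.6% and L(4, 12) = 15.4%, so Grade 4 stops at 4. At 36 enrolled, L(10, 36) = 18.0% and L(11, 36) = 20.4% give 11; L(6, 36) = 9.0% and L(7, 36) = 11.2% give 7. The most that can be affected without a stop is (Grade 3 stop − 1) + (Grade 4 stop − 1), capped at the arm size.

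| Enrolled (CD24Fc) | Stop: Grade 3 / Grade 4 | Most CD24Fc patients affected, no 6.9 stop | 10.4 stops at |
|---|---|---|---|
| 12 (6) | 5 / 4 | 6 of 6 (e.g. 3 + 3) | 5 |
| 24 (12) | 8 / 5 | 7 + 4 = 11 of 12 | 8 |
| 36 (18) | 11 / 7 | 10 + 6 = 16 of 18 (89%) | 11 |
| 72 (36) | 20 / 12 | 19 + 11 = 30 of 36 (83%) | none printed |

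These cover Grades 3 and 4 only. Grade 5 events add nothing to either count, so the other 6 of 36 at full enrolment could be related deaths without triggering 6.9. With Wilson limits the stop counts are 5/3 at 12 and 11/6 at 36, which still allows 6 of 6 and 15 of 18.

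**3. Section 10.4.** With n = CD24Fc patients, the posterior is Beta(0.3 + x, 1.7 + n − x). The probability that the rate exceeds 0.333 is 0.879 for 4 of 6 and 0.973 for 5 of 6; it is 0.951 for 10 of 18 and 0.983 for 11 of 18. The printed limits of 5 and 11 are reproduced. Section 10.4 would therefore stop at 6 of 6 and at 16 of 18 if the events lay outside the irAE spectrum.

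**4. Same limits, cumulative grades, CD24Fc denominator.** Grade 3 or higher: L(3, 6) = 20.1% and L(7, 18) = 23.1%, so stop at 3 of 6 and 7 of 18. Grade 4 or higher: L(3, 6) = 20.1% and L(4, 18) = 10.06%, so stop at 3 of 6 and 4 of 18.

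**5. Chance of ever stopping.** Simulation of 40,000 trials, looks every 6 enrolled (3 per arm) up to 66. True rates are assumed. The last column charges pooled events to half the enrolled.

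| Related rates | 6.9 as written | Cumulative, true CD24Fc arm | Cumulative, pooled events over half |
|---|---|---|---|
| CD24Fc 30% Grade 3, 15% Grade 4; placebo none | about 10% | about 97% | same |
| CD24Fc 20% / 10% / 10% Grade 3 / 4 / 5; placebo none | about 2% | about 93% | same |
| Both arms 10% Grade 3, 5% Grade 4 (no drug effect) | 3 to 4% | about 9% | about 63% |
| CD24Fc 12% Grade 3, 8% Grade 4; placebo none | under 1% | about 23% | same |

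**The case against.** **Section 10.4 is a real backstop.** A reader might infer that nearly every CD24Fc patient could suffer severe related toxicity without Phase II stopping. The documents do not support that. Section 10.4 uses the CD24Fc half, combines Grades 3 to 5, and would stop both examples unless enough events lay inside the irAE spectrum. This limits the gap to irAE-type toxicity but does not close it.

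**The bracketed counts.** Read as hard triggers, 4 and 2 patients allow at most 3 + 1 = 4 affected patients, and the concern disappears. But they contradict the sentence that defines sufficient evidence, so the section needs repair on either reading.

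**Related events also occur on placebo.** In the Phase IIa trial (Section 2.0.1), drug-related TEAEs were reported in 2 of 6 placebo and 1 of 18 CD24Fc patients; in Phase I (Section 2.0.0) in 1 of 10 on placebo. These are all-grade figures, but they show that blinded attribution reaches placebo. The exact halving is thus a worst case. For the same reason, pooled events should not be charged to half the denominator: with an inert drug that stopped about 63% of simulated trials.

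**Two rules, two answers.** A reader might infer that 6.9 and 10.4 contradict each other. At 18 enrolled, four related Grade 4 patients stop under 6.9, while 10.4 continues until 7. But the rules count different events, and stopping if either is met is a natural reading. It is an omission, not a contradiction.

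**Other safeguards.** Section 4.0 takes a patient with related toxicity of grade 3 or higher off therapy, and under Section 13.0 the DSMC meets monthly and discusses all SAEs, which include deaths. These stand, but they set no study-level threshold.

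**Conclusion.** The concern holds for Section 6.9 read alone under its confidence-bound sentence. With Clopper-Pearson limits and related events only on CD24Fc, 6 of 6 CD24Fc patients at 12 enrolled and 16 of 18 at 36 could have related Grade 3 or 4 toxicity without a stop, and related deaths never count. Because 10.4 covers new AEs of grade 3 or higher outside the irAE spectrum, what is exposed is CD24Fc-related severe or fatal toxicity inside it. At assumed true CD24Fc rates 1.5 times each limit (30% and 15%), 6.9 stops only about one trial in ten. The figures depend on the interval method, which the protocol leaves open, and on setting aside bracketed counts that cannot be squared with the bound. Phase II as a whole is not unmonitored.

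**What to change.** In Section 6.9:

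- Make the rates cumulative: Grade 3 or higher, and Grade 4 or higher including death.
- Have the unblinded statistician apply the rule for the DSMC to actual CD24Fc-arm events over patients treated with CD24Fc. Do not charge pooled placebo events to half the denominator.
- Name the interval method.
- Reconcile the bracketed 4 and 2 patients with the confidence-bound sentence.
- State how 6.9 and 10.4 combine, for example that the trial stops if either is met.

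The 20%, 10% and 33.3% limits are the sponsor's to reconcile.

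The cost is protocol wording plus an unblinded count held for the DSMC. The rule also triggers earlier. With no drug effect and assumed 10%/5% related rates in both arms, false stops rise from 3 to 4% to about 9%. With true CD24Fc rates of 20% for Grade 3 or higher and 8% for Grade 4 or higher, at or just under the limits, about 23% of trials would stop, against under 1% now. The sponsor should review these operating characteristics before fixing the limits.

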7. STUDY CALENDAR

Baseline evaluations are to be conducted within 14 days prior to 1st infusion unless otherwise noted. Please see [Tables 1](#) and [2](#).

8. CRITERIA FOR EVALUATION AND ENDPOINTS DEFINITIONS

8.0 Definitions

8.0.0 Evaluable For Toxicity

All patients will be evaluable for toxicity from the time of their first treatment with CD24Fc up to 30 days after completion of last dose of treatment.

8.0.1 Acute Toxicity

All patients will be evaluable for toxicity from the drug. All patients will be monitored for 1-hour post infusion with a registered nurse or nurse practitioner within immediate proximity.

8.0.2 Evaluable For Response

8.0.2.0 Tumor Evaluation

All patients will be considered evaluable for response according to RECIST 1.1. For this study, PSA-only disease is included in Non-Measurable disease.

8.1 Response and Evaluation Endpoints

Response and progression will be evaluated in this study using the new international criteria proposed by RECIST committee. Changes in only the largest diameter (unidimensional measurement) of the tumor lesions are used in the RECIST 1.1 criteria.

8.1.0 Measurable Disease

Measurable lesions are defined as those that can be accurately measured in at least one dimension (longest diameter to be recorded) as ≥ 20 mm with conventional techniques (PE, CT, XR, MRI) or as ≥ 10 mm with spiral CT scan. All tumor measurements must be recorded in millimeters (or decimal fractions of centimeters).

8.1.1 Non-Measurable Disease

All other lesions (or sites of disease), including small lesions (longest diameter < 20 mm with conventional techniques or < 10 mm with spiral CT scan) are considered non-measurable disease. Bone lesion, leptomeningeal disease, ascites, pleural/pericardial effusions, lymphangitis cutis/pneumonitis, inflammatory breast disease, abdominal masses (not followed by CT or MRI) and cystic lesions are all non-measurable. Prostate cancer patients may also have PSA-only disease.

8.1.2 Target Lesions

All measurable lesions up to a maximum of 2 lesions per organ and 5 lesions in total representative of all involved organs should be identified as target lesions and be recorded and measured at baseline. Target lesions should be selected on the basis of their size (lesions with the longest diameter) and their suitability for accurate repetitive measurements (either by imaging techniques or clinically). A sum of the longest diameter (LD) for all target lesions will be calculated and reported as the baseline sum LD. The baseline sum LD will be used as reference to further characterize the objective tumor response of the measurable dimension of the disease. If there are > 10 measurable lesions, those not selected as target lesions will be considered together with non-measurable disease as non-target lesions (see section 10.2.4).

8.1.3 Non-Target Lesions

All non-measurable lesions (or sites of disease) plus any measurable lesions over and above the 10 listed as target lesions. Measurements are not required but these lesions should be noted at baseline and should be followed as “present” or “absent”. The exception for this requirement is the serial evaluation of prostate specific antigen (PSA) levels in the serum. Although PSA values constitute “non-target” disease, in this study which includes a population of patients with hormone refractory prostate cancer, PSA levels are expected to be the principal measure of disease activity and response to therapy, if any.

8.1.4 Response

All patients will have their BEST RESPONSE on study classified as outlined below:

Complete Response (CR): disappearance of all clinical and radiological evidence of tumor (both target and non-target).

Partial Response (PR): at least a 30% decrease in the sum of LD of target lesions taking as reference the baseline sum LD. Patients may not demonstrate clinical or radiographic evidence of progression of measurable or non-measurable disease during this time period.

Stable Disease (SD): steady state disease. Neither sufficient shrinkage to qualify for PR nor sufficient increase to qualify for PD.

Progressive Disease (PD): at least a 20% increase in the sum of LD of measured lesions taking as reference the smallest LD recorded since the treatment started or the appearance of one or more new lesions.

In exceptional circumstances unequivocal progression of non-target lesions may be accepted as evidence of disease progression.

Table 4: Evaluation for tumor response

Target Lesions	Non-Target Lesions	New Lesions	Overall Response	Best Response For This Category Also Requires
CR	CR	No	CR	≥ 4 weeks confirmation
CR	Non-CR/Non-PD	No	PR	≥ 4 weeks confirmation
PR	Non-PD	No	PR	≥ 4 weeks confirmation
SD	Non-PD	No	SD	Documented at least ≥ 4 weeks from baseline; ≥ 8 weeks for PSA-only disease
PD	Any	Yes or No	PD	No prior SD, PR, or CR
Any	PD	Yes or No	PD	No prior SD, PR, or CR
Any	Any	Yes	PD	No prior SD, PR, or CR

NOTE: Patients with global deterioration of health status requiring discontinuation of treatment without objective evidence of disease progression at that time should be reported as “symptomatic deterioration”. Every effort should be made to document the objective progression even after discontinuation of treatment.

8.1.4.0 Response Duration

Response duration will be measured from the time measurement criteria for CR/PR (whichever is first recorded) are first met until the first date that recurrent or progressive disease is objectively documented.

8.1.4.1 Stable Disease Duration

Stable disease duration will be measured from the time of start of therapy until the criteria for progression are met, taking as reference the smallest measurements recorded since the treatment started.

8.1.4.2 Methods of Measurement

The same method of assessment and the same technique should be used to characterize each identified and reported lesion at baseline and during follow-up.

9. SPECIAL INSTRUCTIONS

A blood sample of 20-30 ml is to be drawn as outlined in study flow charts (Table 1 and Table 2). Each sample will be collected into a non-heparinized vacutainer with a 20 g or larger needle. Blood samples will be shipped at room temperature until processed to separate the plasma. Serological studies will be performed in all patients during the course of this study to assess the changes in HMGB1 level before, during and after the treatment. The sample should be sent to for on-site processing and storage:

[name]., Ph.D.

10. STATISTICAL CONSIDERATIONS

10.0 Endpoints

10.0.0 Primary Endpoints

Phase I: Event of new AE of \geq grade 3 that are outside the spectrum of irAEs when CD24Fc is given in cancer patients who developed grade 2-3 irAEs.

Phase II: Co-primary endpoints:

- Recovery rate (as defined by reduction of irAE by one grade) at Day 42.
- Time to recovery from grade 2 or 3 irAE (as defined by reduction of at least 1 grade in irAE severity) from the initiation of CD24Fc treatment. Patients who have not been documented to have event (reduction of at least 1 grade) will be censored at the date of the latest clinical assessment that documented as being free of event.

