10.0.1 Secondary Endpoints

Phase I:

- Time to irAE reduction by at least 1 grade from the initiation of CD24Fc treatment.

- Time to all irAEs reduced to ≤ 1 (by NCI CTCAEv5.0) from the initiation of CD24Fc treatment.
- Time to resume ICI treatment from the initiation of CD24Fc treatment.
- Recovery rate (reduction of irAE by one grade) at D42.

Patients who have not been documented to have above events will be censored at the date of the latest clinical assessment that documented as being free of events.

Phase II:

- Time to all irAEs reduced to ≤ 1 (by NCI CTCAEv5.0) from the initiation of CD24Fc treatment. Patients who have not been documented to have the event will be censored at the date of the latest clinical assessment that documented as being free of event.
- The use of steroids and other drugs (drug, dose, duration).
- Overall response rate (ORR) after retreatment with ICI with or without CD24Fc after resolution of irAE.
- Progression free survival (PFS) will be calculated as the time from initiation of ICI to first documented evidence of disease progression or death, whichever comes first. Alive patients who have not been documented to have progression will be censored at the date of the latest clinical assessment that documented as being free of progression.
- Overall survival (OS) will be calculated as the time from diagnosis to death. Alive patients will be censored at the date of the latest follow-up visit.

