10.1 Randomization for Phase II Study

Steroids is the most commonly used SOC therapy for irAEs. It affects the severity and duration of irAE, which are the key endpoints of this study. We thus will stratify the subjects based on the status of steroids use at registration. Stratified block randomization will be used. Randomization codes will be generated in a permuted block design, stratified by the status of steroids use at registration. The block size will be balanced within each block to maintain a 1:1 ratio between the two groups. For patient who have no steroids use at registration but start on steroids before starting CD24Fc treatment, the patient will be moved to the steroid stratum. If a subject withdraws from participation in the study or changed to steroids use group, his or her randomization code will not be re-used.

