10.2 Statistical Analysis

Demographic and background characteristics obtained at enrollment will be listed and summarized. Descriptive statistics will be used to summarize changes of biomarkers from baseline in clinical laboratory parameters for this cohort, and use of steroids (drug, dose, duration) and other treatment for irAE. We will adjust steroids use in analyses. Subgroup analyses will be performed separately by the status of Steroids use.

To assess toxicity: Toxicity is evaluated by NCI CTCAEv5.0. The type, grade, frequency and proportion of toxicities noted during the treatment period will be reported, along with associated 95% confidence interval of proportion. All adverse events noted by the investigator will be tabulated according to the affected body system. In phase I lead-in study, dose limiting toxicity is defined as any new AE of \geq grade 3 that are outside the spectrum of irAEs.

To assess time to recovery from irAE (time to reduction of irAE by at least one grade), time to all irAEs reduced to ≤ 1 , and time to resume ICI treatment: All time points will be started from Day 1 of CD24Fc treatment. Kaplan-Meier plots and confidence intervals will be used to summarize outcomes. Medians and associated 95% confidence intervals will be calculated, and comparisons between groups will be

performed by log-rank tests. Cox proportional hazard models will be used to explore association between covariates and outcomes.

To assess recovery rate of CD24Fc (reduction of irAE by at least one grade) at D42 and response rate of ICI: The fraction of patients who experience a PR or CR will be determined by dividing the number of responders by the total evaluable patients. The fraction will be reported along with 95% two-sided confidence intervals. Comparisons between groups will be performed by Fisher's Exact tests. We will also characterize the proportion who remain that either respond or have stable disease, compared to those who progress.

To assess PFS and OS: Kaplan-Meier plots and confidence intervals will be used to summarize PFS, and OS; 1-year OS rate will be reported; medians and associated 95% confidence intervals will be calculated, and comparisons between groups will be performed by log-rank tests. Cox PH models will be used to explore association between outcomes and covariates.

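### Patients who die without the event are censored, so the planned Kaplan-Meier curves overstate recovery (slightly) and ICI resumption (possibly by more)

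*Combined protocol and SAP*

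**What the plan says.** Time to recovery is a Phase II co-primary endpoint. Under Section 10.0.0, a patient with no documented one-grade reduction "will be censored at the date of the latest clinical assessment that documented as being free of event". The synopsis words this co-primary as a Kaplan-Meier estimate, so the estimator is part of the endpoint.

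Section 10.0.1 repeats the rule for Phase II time to all irAEs at grade 1 or less: "Patients who have not been documented to have the event will be censored at the date of the latest clinical assessment". For Phase I, one sentence covers all the listed time endpoints, including time to resume ICI: "Patients who have not been documented to have above events will be censored at the date of the latest clinical assessment".

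Time to resume ICI is also a Phase II endpoint in the synopsis and in Section 0.1.1. The Phase II list in Section 10.0.1 omits it, so no Phase II censoring rule is written for it.

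For all three endpoints Section 10.2 states: "Kaplan-Meier plots and confidence intervals will be used to summarize outcomes". It adds medians and log-rank tests. No competing-risk method appears. By contrast, Section 10.0.1 names death explicitly in the definitions of PFS and OS.

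**The concern.** Recovery and ICI resumption are non-fatal events, and death rules them out. Kaplan-Meier with deaths censored assumes that those who died would have gone on to recover or restart at the same rate as those still under follow-up. One minus the curve then describes a setting without death, not the proportion of enrolled patients who recover or resume.

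Deaths cannot be taken as negligible. Section 5 describes stage IV, incurable disease, and Section 5.0 requires only 3 months of life expectancy. Unresolved irAEs are followed past Day 60 (footnote 4 to Tables 1 and 2), and chart checks run to 1 year (Section 6.1.1). ICI is barred during the study period (Section 6.5) and retreatment is evaluated at Day 42, so death has a long time in which to pre-empt resumption. Section 6.6 also lets patients with progression leave, and these patients may be unlikely to restart ICI.

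At stake are the reported probabilities and medians. If deaths differed between arms, the curves for these endpoints would not show the patients lost to death.

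**Working it through.** **Plan's own figure.** Section 10.3 states: "A sample size of 72 patients (36 in each arm) will have 81% power" for 50% against 80%, and "This result is based on one-sided Fisher's Exact test and significance level of 0.05". Exact enumeration over two binomials with 36 per arm gives 80.9%, so the figure reproduces. It concerns the Day 42 proportion and does not depend on the censoring rule.

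**Inputs.** From the plan: recovery at Day 42 of 50% (control) and 80% (CD24Fc). Assumed, because the documents give no figure: constant hazards, 1-year OS from 90% to 30%, and the resumption rates below.

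**Formulas.** Let λr be the event hazard and λd the death hazard per day.
- True cumulative incidence: CIF(t) = λr/(λr+λd) × [1 − exp(−(λr+λd)t)].
- One minus Kaplan-Meier with deaths censored: 1 − exp(−λr·t).
- λd = −ln(1-year OS)/365, and λr is solved so that CIF(42) equals the plan's 50% or 80%.

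**Worked case: 1-year OS 50% (median OS 12 months), true recovery 50% at Day 42.** λd = 0.6931/365 = 0.00190; the solution is λr = 0.01736.
- Day 42: CIF = 0.901 × (1 − e^−0.809) = 50.0%; Kaplan-Meier = 1 − e^−0.729 = 51.8%.
- Day 60: CIF = 0.901 × (1 − e^−1.156) = 61.8%; Kaplan-Meier = 1 − e^−1.042 = 64.7%.
- Median: 42 days by construction; Kaplan-Meier gives 0.6931/0.01736 = 39.9 days.

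**Excess of one minus Kaplan-Meier at Day 42, in points**

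| 1-year OS | True 50% | True 80% |
|---|---|---|
| 90% | 0.3 | 0.4 |
| 70% | 0.9 | 1.2 |
| 50% | 1.8 | 2.3 |
| 30% | 3.1 | 4.0 |

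At 1-year OS of 50% in both arms, the arm difference is 30.0 points in truth and 30.5 by Kaplan-Meier.

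**ICI resumption at 1 year.** Resumption is taken as possible from Day 42, which leaves 365 − 42 = 323 days. True incidence = exp(−42λd) × CIF(323); Kaplan-Meier = 1 − exp(−323λr). λr is solved for true resumption of 20% or 50%.

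| Removed by competing event in 1 year | True 20% | True 50% |
|---|---|---|
| 20% | Kaplan-Meier 22.5% (+2.5) | 55.8% (+5.8) |
| 30% | 24.1% (+4.1) | 59.4% (+9.4) |
| 50% | 28.5% (+8.5) | 68.5% (+18.5) |

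**A simpler illustration, with resumption possible from Day 1.** Take a resumption median of 180 days absent death and a median OS of 12 months. Kaplan-Meier at 1 year = 1 − 2^(−365/180) = 75%. CIF = 365/545 × (1 − 2^(−365/180 − 1)) = 0.670 × 0.877 = 59%. If the other arm has the same resumption hazard but a 6-month median OS, its Kaplan-Meier value is still 75% and its CIF is 182.5/362.5 × (1 − 2^(−365/180 − 2)) = 0.503 × 0.939 = 47%. The 12-point gap does not appear in the curves.

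**Living patients who never resume.** Suppose 50% never resume and the rest restart between Day 42 and Day 120. If all never-resumers stay in follow-up to 1 year, Kaplan-Meier gives 50%, which is correct. If half of them are censored at Day 60 it gives 65%; if all are, 100%. Early exit causes the bias; being unable to resume does not.

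**The case against.** The strongest case on the other side is that little turns on this. The bias in the co-primary at Day 42 is at most about 4 points over the assumed range, and the arm difference hardly moves when deaths are balanced. The sample size rests on the binary endpoint. PFS and OS are compared by arm, so a mortality imbalance would be seen there. All of this stands, and it limits the point to estimation.

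Three stronger readings are tempting, and the documents do not support them.
- A reader might infer that every patient who can no longer restart ICI inflates the curve. A living patient permanently off ICI remains in the risk set until the last assessment and counts against the arm. The bias needs death or early exit.
- A reader might infer that Phase II has a written rule censoring deaths for time to resume ICI. That rule is written only for Phase I (n=6). For Phase II it is an inference from the planned analysis, and the omission is itself a gap.
- A reader might infer that the log-rank test is wrong and must be replaced. With deaths censored it validly compares cause-specific hazards. A Gray-type test answers a different question, because it lets mortality enter the recovery comparison. Which should lead is a choice of estimand.

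Nor should the 3-month life expectancy be read as a median survival. It is an entry minimum, set alongside ECOG below 2.

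**Conclusion.** The point holds as one about estimation. As written, the rule censors patients who die without the event, and Kaplan-Meier then overstates the probability and shortens the median. For recovery the effect is small: about 0.3 to 4 points at Day 42 for 1-year OS of 90% to 30%, and about 65% against 62% at Day 60 with a 12-month median OS. For 1-year ICI resumption it can be larger: about 2.5 to 18.5 points over the ranges tabulated. These sizes rest on assumed constant hazards and on death and resumption rates that the documents do not give; only the direction is independent of those rates. The plan's main test of the Day 42 recovery rate is not in question.

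**What to change.** In Sections 10.0.0, 10.0.1 and 10.2:
- Name death as a competing event for time to recovery, time to all irAEs at grade 1 or less, and time to resume ICI. Censor only patients who are alive and event-free at last assessment.
- Report Aalen-Johansen cumulative incidence by arm, with confidence intervals and medians taken from it, in place of one minus Kaplan-Meier. Align the synopsis wording of the co-primary.
- Keep the log-rank test as the cause-specific comparison, and add a Gray-type test as a supplement.
- Add time to resume ICI to the Phase II list in Section 10.0.1 under the same rule.
- Report by arm how many patients left before the event and when, since naming death does not repair early exit.

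The cost is plan wording and standard software, with no change to design or sample size. Displayed percentages will be slightly lower, and a median may not be reached where cumulative incidence stays below 50%.
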